6.18.1. Extent of Exposure

Duration of exposure (in days) to study drug will be summarized by treatment period with corresponding safety population, which is defined in [Table JAHV.6.10](#).

Total PY of exposure will be reported for overall duration of exposure. Descriptive statistics (n, mean, standard deviation [SD], minimum, 1st quartile, median, 3rd quartile and maximum) will be provided for patient-days of exposure, and the frequency of patients falling into different exposure ranges will be summarized. Exposure ranges will generally be reported in weeks using the following as a general guide:

- ≥ 4 weeks, ≥ 16 weeks, ≥ 26 weeks, ≥ 52 weeks

- >0 to <4 weeks, \geq 4 weeks to <16 weeks, \geq 16 weeks to <26 weeks, \geq 26 to <52 weeks, and \geq 52 weeks

Overall exposure will be summarized in total PY which is calculated according to the following formula:

$$PYE = \text{sum of duration of exposure in days (for all patients in treatment group)} / 365.25$$

6.18.2. Adverse Events

Adverse events are recorded in the eCRFs. The planned summaries are provided in [Table JAHV.6.11](#) and are described more fully in compound-level safety standards and in the adverse event-related PhUSE white paper [Analysis and Displays Associated with Adverse Events: Focus on Adverse Events in Phase 2-4 Clinical Trials and Integrated Summary Document (PhUSE 2017)]. The analysis population and period are defined in [Table JAHV.6.11](#), and by-treatment analysis will provided for the DBW safety population in the DBW period.

If study drug is temporarily interrupted and subsequently restarted during the treatment period, the measurements taken during the temporary interruption will be included in the analysis. Where applicable, the time elapsed during the temporary interruption will also be included in analyses.

For events that are gender-specific (as defined by the MedDRA), the denominator and computation of the percentage will include only patients from the given sex.

Table JAHV.6.11. Summary Tables Related to Adverse Events

Analysis
An overview table, with the number and percentage of patients in the safety set with death, an SAE, any TEAE, discontinuation from the study due to an AE, permanent discontinuation from study drug due to an AE, or a severe TEAE
The number and percentages of patients with TEAEs will be summarized using MedDRA Preferred Term nested within System Organ Class.
The number and percentages of patients with TEAEs will be summarized using MedDRA Preferred Term.
The number and percentages of patients with TEAEs will be summarized using MedDRA Preferred Term for the common TEAEs (occurring in \geq 1%, before rounding, of treated patients).
The number and percentages of patients with TEAEs by maximum severity will be summarized using MedDRA Preferred Term for the common TEAEs. Only counts and percentages will be included for the TEAEs by maximum severity.
A listing of all deaths will be provided.
The number and percentage of patients who experienced a serious adverse event (including deaths and SAEs temporally associated or preceding deaths) will be summarized using MedDRA Preferred Term nested within System Organ Class.
A listing of SAEs will be provided.
The number and percentage of patients who permanently discontinued from study drug due to an adverse event (including adverse events that led to death) will be summarized using MedDRA Preferred Term nested within System Organ Class.
The number and percentage of patients who temporarily interrupted study drug due to an adverse event will be summarized using MedDRA Preferred Term nested within System Organ Class.

Abbreviations: AE=adverse event; MedDRA = Medical Dictionary for Regulatory Activities; SAE = serious adverse event; TEAE = treatment emergent adverse event.

6.18.3. Clinical Laboratory Evaluation

The planned summaries for clinical laboratory evaluations are provided in [Table JAHV.6.12](#) and are described more fully in compound-level safety standards and in the laboratory-related PhUSE white papers [Analyses and Displays Associated with Measures of Central Tendency – Focus on Vital Sign, Electrocardiogram, and Laboratory Analyte Measurements in Phase 2-4 Clinical Trials and Integrated Submission Documents (PhUSE 2013) and Analyses and Displays Associated with Outliers or Shifts from Normal to Abnormal: Focus on Vital Signs, Electrocardiogram, and Laboratory Analyte Measurements in Phase 2-4 Clinical Trials and Integrated Summary Documents (PhUSE 2015)]. The analysis population and period are defined in [Table JAHV.6.12](#), and by-treatment analysis will provided for the DBW safety population in the DBW period.

There is one special circumstance for laboratory values to be derived. The low-density lipoprotein (LDL)/high-density lipoprotein (HDL) ratio will be derived as the ratio of LDL cholesterol to HDL cholesterol. Similarly, the ratio of HDL to LDL will be derived. There are no central laboratory reference ranges for the LDL/HDL or HDL/LDL ratio.

For the categorical laboratory analyses (shift and treatment-emergent), the analysis period is defined as the treatment period plus up to 30 days off-drug follow-up time. The analysis period for the continuous by-visit laboratory analyses including change from baseline by visit and to last observation is defined as the treatment period excluding off-drug follow-up time.

Table JAHV.6.12. Summary Tables Related to Clinical Laboratory Evaluations

Analysis
Box plots for observed values by visit and change from baseline by visit.
Tables with number and percentages of patients who shift from normal/high to low (ie, treatment-emergent low) and number and percentages of patients who shift from normal/low to high (ie, treatment-emergent high)
Listing of abnormal findings for laboratory analyte measurements, including qualitative measures

6.18.4. Vital Signs and Other Physical Findings

The planned summaries for vital signs and physical measurement (systolic blood pressure [BP], diastolic BP, pulse, weight, , height, body mass index [BMI], temperature) are provided in [Table JAHV.6.13](#) and are described more fully in compound-level safety standards and in the vitals-related PhUSE white papers [Analyses and Displays Associated with Measures of Central Tendency – Focus on Vital Sign, Electrocardiogram, and Laboratory Analyte Measurements in Phase 2-4 Clinical Trials and Integrated Submission Documents (PhUSE 2013) and Analyses and Displays Associated with Outliers or Shifts from Normal to Abnormal: Focus on Vital Signs, Electrocardiogram, and Laboratory Analyte Measurements in Phase 2-4 Clinical Trials and Integrated Summary Documents (PhUSE 2015)].

Table JAHV.6.13. Summary Tables Related to Vital Signs

Analysis
Box plots for observed values by visit and change from baseline by visit.
Tables with number and percentages of patients who shift from normal/high to low (ie, treatment-emergent low) and percentages of patients who shift from normal/low to high (ie, treatment-emergent high). The limits are defined in the compound-level safety standards and are based on literature.

For vital signs and physical characteristics, original-scale data will be analyzed. Mean changes from baseline and as incidence of abnormal values will be summarized. The observed values at each visit (starting at OLLI baseline) and change from baseline to each scheduled visit, respectively, will be displayed in box plots for patients by treatment period with the corresponding safety population. These box plots will be used to evaluate trends over time and to assess a potential impact of outliers on central tendency summaries. The scheduled visits/measurements will be included. The unscheduled visits and the repeat measurements will be excluded.

Table JAHV.6.14. Categorical Criteria for Abnormal Treatment-Emergent Blood Pressure and Pulse Measurements for Children and Adolescents

Age (years)		Systolic BP, mm Hg (supine or sitting forearm at heart level)	Diastolic BP, mm Hg (supine or sitting forearm at heart level)	Pulse/HR bpm (supine or sitting)
Child 2-4	Low	≤75 (low limit) and decrease from lowest value during baseline ≥15 if >75 at each baseline visit	≤40 (low limit) and decrease from lowest value during baseline ≥10 if >40 at each baseline visit	<60 (low limit) and decrease from lowest value during baseline ≥25 if ≥60 at each baseline visit
	High ^a	≥110 (high limit) and increase from highest value during baseline ≥15 if <110 at each baseline visit	≥76 (high limit) and increase from highest value during baseline ≥10 if <76 at each baseline visit	>160 (high limit) and increase from highest value during baseline ≥25 if ≤160 at each baseline visit
Child 5-9	Low	≤80 (low limit) and decrease from lowest value during baseline ≥15 if >80 at each baseline visit	≤45 (low limit) and decrease from lowest value during baseline ≥10 if >45 at each baseline visit	<60 (low limit) and decrease from lowest value during baseline ≥25 if ≥60 at each baseline visit
	High ^a	≥119 (high limit) and increase from highest value during baseline ≥15 if <119 at each baseline visit	≥78 (high limit) and increase from highest value during baseline ≥10 if <78 at each baseline visit	>150 (high limit) and increase from highest value during baseline ≥25 if ≤150 at each baseline visit
Child 10-12	Low	≤85 (low limit) and decrease from lowest value during baseline ≥20 if >85 at each baseline visit	≤50 (low limit) and decrease from lowest value during baseline ≥10 if <50 at each baseline visit	<60 (low limit) and decrease from lowest value during baseline ≥25 if ≥60 at each baseline visit
	High ^a	≥126 (high limit) and increase from highest value during baseline ≥20 if <126 at each baseline visit	≥82 (high limit) and increase from highest value during baseline ≥10 if <82 at each baseline visit	>140 (high limit) and increase from highest value during baseline ≥25 if ≤140 at each baseline visit
Adolescent 13 - 17	Low	≤90 (low limit) and decrease from lowest value during baseline ≥20 if >90 at each baseline visit	≤50 (low limit) and decrease from lowest value during baseline ≥10 if >50 at each baseline visit	<50 (low limit) and decrease from lowest value during baseline ≥15 if ≥50 at each baseline visit
	High ^a	≥129 (high limit) and increase from highest value during baseline ≥20 if <129 at each baseline visit	≥86 (high limit) and increase from highest value during baseline ≥10 if <86 at each baseline visit	>120 (high limit) and increase from highest value during baseline ≥15 if ≤120 at each baseline visit

Abbreviations: BP = blood pressure; HR = heart rate.

^a The high limit values shown in this table correspond to 95th percentile for the age group under the 2017 American College of Cardiology/American Heart Association task Force on Clinical Practice Guidelines revised criteria for hypertension. Values higher than 95th percentile are consistent with Stage 1 or Stage 2 hypertension. Under some circumstances it may be appropriate to conduct analyses considering only the change from baseline reference limit.

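### The low diastolic criterion for ages 10–12 has its baseline inequality reversed, so a fall from normal is never flagged and an already-low child can be counted as treatment-emergent

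*SAP*

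**What the plan says.** SAP Section 6.18.4 plans two categorical summaries for vital signs, treatment-emergent low and treatment-emergent high. Table JAHV.6.13 describes the first as the number and percentage of "patients who shift from normal/high to low (ie, treatment-emergent low".

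Table JAHV.6.14 gives the working criteria by age band. For diastolic pressure, Low:

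- Ages 2–4: "≤40 (low limit) and decrease from lowest value during baseline ≥10 if >40 at each baseline visit"
- Ages 5–9: "≤45 (low limit) and decrease from lowest value during baseline ≥10 if >45 at each baseline visit"
- Ages 10–12: a limit of ≤50, and "decrease from lowest value during baseline ≥10 if <50 at each baseline visit"
- Ages 13–17: "≤50 (low limit) and decrease from lowest value during baseline ≥10 if >50 at each baseline visit"

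In the 10–12 row, the systolic Low cell reads "≤85 (low limit) and decrease from lowest value during baseline ≥20 if >85 at each baseline visit".

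Section 6.18.4 also says that the limits come from the compound-level safety standards, which are a separate document.

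**The concern.** The clause on baseline visits keeps out children who were already low before treatment, so that what is counted is new. In the 10–12 diastolic cell the inequality points the other way. It admits only children who were below 50 throughout baseline and shuts out every child who started above 50.

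The criterion feeds several outputs. Table JAHV.6.10 applies treatment-emergent abnormal vital signs to the open-label periods (general safety population) and to the withdrawal period (DBW safety population, baricitinib against placebo). Section 6.21.1 lists treatment-emergent high and low vital signs among the summaries for the data monitoring committee. A literally coded cell would probably show few or no events, which looks plausible and would not draw attention.

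**Working it through.** The plan states no figure to reproduce here. The check is of logic, against the rest of the same table.

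**1. The twelve Low cells of Table JAHV.6.14** (limit / required fall / baseline condition)

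| Age | Systolic | Diastolic | Pulse |
|---|---|---|---|
| 2–4 | ≤75 / ≥15 / >75 | ≤40 / ≥10 / >40 | <60 / ≥25 / ≥60 |
| 5–9 | ≤80 / ≥15 / >80 | ≤45 / ≥10 / >45 | <60 / ≥25 / ≥60 |
| 10–12 | ≤85 / ≥20 / >85 | **≤50 / ≥10 / <50** | <60 / ≥25 / ≥60 |
| 13–17 | ≤90 / ≥20 / >90 | ≤50 / ≥10 / >50 | <50 / ≥15 / ≥50 |

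Eleven cells require a baseline on the normal side of the limit, and one does not. The 13–17 diastolic cell differs from it only in the sign.

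**2. What the printed cell implies.** Let L be the lowest baseline value and P the post-baseline value. The rule as printed needs P ≤ 50, L − P ≥ 10, and every baseline value below 50, so L < 50. Then P ≤ L − 10 < 40. The stated limit of 50 can never decide a case; on whole-number readings the highest value that can be flagged is 39. A rule whose own limit never operates is unlikely to be deliberate.

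**3. Individual cases** (one baseline value standing for all baseline visits)

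| Baseline → post | As printed (<50) | With >50 |
|---|---|---|
| 62 → 45 (fall 17) | not flagged | flagged |
| 65 → 45 (fall 20) | not flagged | flagged |
| 60 → 50 (fall 10) | not flagged | flagged |
| 48 → 38 (fall 10) | flagged | not flagged |
| 49 → 39 (fall 10) | flagged | not flagged |
| 45 → 40 (fall 5) | not flagged | not flagged |
| 50 → 40 (fall 10) | not flagged | not flagged |

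**4. Enumeration.** Take all whole-number pairs with baseline 30–90 and post-baseline 20–90 mm Hg. These ranges are assumed, and the counts show the logic rather than expected frequencies.

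- As printed: baselines 30 to 49 contribute 1, 2, …, 20 pairs, total 20 × 21 / 2 = 210, all with baseline below 50.
- With >50: baselines 51 to 59 contribute 22, …, 30 pairs, total 9 × 26 = 234. Baselines 60 to 90 contribute 31 pairs each, total 31 × 31 = 961. The sum is 1195, all with baseline above 50.
- The two sets share no pair.

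**5. Who is covered.** The band spans 3 of the 16 years from 2 to under 18. With ages evenly spread, 3/16 = 18.75%, and 0.1875 × 128 = 24 randomized patients. The same share of the 197 planned for the lead-in is 0.1875 × 197 ≈ 37. The even spread is an assumption. If the share were 10% or 30%, the randomized count would be about 13 (0.10 × 128) or 38 (0.30 × 128). These are the children to whom the criterion applies. Only those with a qualifying reading would be misclassified, and the documents do not allow that number to be estimated.

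**The case against.** The best reply is that this is an obvious slip which practice would catch. Table JAHV.6.13 states the governing idea, eleven neighbouring cells show the intended direction, and the limits are said to be defined in the compound-level standards, which may carry the right sign. A validating programmer has good grounds to query the cell, so the harm is conditional on literal coding. Section 6.18.4 also plans box plots of observed values and changes by visit, Section 6.18 says listings will hold all safety data, and its p-values are offered only as flags. A low diastolic reading would not vanish from the trial.

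Most of this stands as a limit on the consequence. None of it repairs the printed rule. Table JAHV.6.14 is the specification in this SAP, and if the standards disagree with it, that conflict needs resolving too. The footnote permitting an analysis on change alone is attached to the High limits and applies only in unspecified circumstances.

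A second reply is that the baseline clause might only switch on the required fall, so that a normal-baseline child would be flagged by the limit alone. Read that way, the other eleven cells would flag already-low children who had not fallen at all, against Table JAHV.6.13. The reading fails.

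The figure of 24 patients is soft. Enrolment was staggered with older groups first, and protocol Appendix 7 shows the youngest cohort not yet started, so an even spread of ages is doubtful. The defect does not depend on it.

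**Conclusion.** The concern holds. As written, the 10–12 diastolic Low cell cannot detect a new low value in a child whose baseline was normal. The only children it can count are those already below 50 at every baseline visit who fall a further 10 mm Hg or more. Within this one categorical summary and age band, sensitivity to a true shift from normal is zero, and every flagged case is a misclassification under the SAP's own definition.

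This rests on reading the baseline clause as an eligibility condition, the only reading consistent with the rest of the table, and on the cell being programmed as printed. The scope is one cell of a descriptive safety table. It is a minor point with no bearing on time to flare, the significance level or the sample size, but it determines which children are reported.

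**What to change.** In SAP Table JAHV.6.14, diastolic Low for ages 10–12, change <50 to >50, matching the 13–17 cell. Confirm the sign in the compound-level safety standards, check the criterion actually coded, and rerun any output already produced from the printed version, including summaries sent to the data monitoring committee. The cost is one character in the SAP and the programming specification, plus that check. No new data are needed.

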6.18.4.1. Standardized Growth

Weight, height, and BMI data will be merged to the Centers for Disease Control and Prevention (CDC) standard growth data (released in 2000) by age and gender in order to compare patients’ growth with the standard. Z-score and standardized percentile of weight, height, and BMI at each visit will be calculated based on the 2000 CDC growth charts.

The z-score and percentile calculations are based on algorithms and data provided by the National Center for Health Statistics. The details are provided in the CDC website (<https://www.cdc.gov/nccdphp/dnpao/growthcharts/resources/sas.htm>).

- The following summaries will be provided by treatment period with the corresponding safety population: baseline, mean change of actual measure, z-score and standardized percentile of weight, height, and BMI will be summarized.
- Patients’ mean weight, height, and BMI standardized percentile will be plotted versus investigational product exposure time.

By-patient listings of actual measures, z-scores, standardized percentiles in weight, height, and BMI for each visit will be provided.

6.18.5. Special Safety Topics, including Adverse Events of Special Interest

In addition to general safety parameters, safety information on specific topics of special interest will also be presented. Additional special safety topics may be added as warranted. The topics outlined in this section include the protocol-specified AESI.

In general, for topics regarding safety in special groups and circumstances, patient profiles and/or patient listings, where applicable, will be provided when needed to allow for medical review of the time course of cases/events, related parameters, patient demographics, study drug treatment, and meaningful concomitant medication use. In addition to the safety topics for which provision or review of patient data are specified, these will be provided when summary data are insufficient to permit adequate understanding of the safety topic.

The analysis and summary will be provided by treatment period with the corresponding safety population, where the detailed definition of the population and baseline can be found in Section 6.1.1 and [Table JAHV.6.10](#).

6.18.5.1. Abnormal Hepatic Tests

Hepatic labs include alanine aminotransferase (ALT), aspartate transaminase (AST), total bilirubin (TBL), and serum alkaline phosphatase (ALP). When criteria are met for hepatic evaluations, investigators will complete a follow-up hepatic safety eCRF. The planned summaries are provided in [Table JAHV.6.15](#).

Table JAHV.6.15. Summary Tables Related to Hepatic Safety

Analysis
ALT and AST: The number and percentages of patients with a measurement greater than or equal to 3 times (3X), 5 times (5X), and 10 times (10X) the central lab upper limit of normal (ULN) for all patients with a postbaseline value and for subsets based on various levels of baseline value.
TBL: The number and percentages of patients with a measurement greater than or equal to 2 times (2X) the central lab ULN will be summarized for all patients with a postbaseline value and for subsets based on various levels of baseline value.

ALP: The number and percentages of patients with a measurement greater than or equal to 1.5 times (1.5X) the central lab ULN will be summarized for all patients with a postbaseline value and for subsets based on various levels of baseline value.
Plot of maximum postbaseline ALT vs. maximum postbaseline total bilirubin.
Patient profiles including demographics, disposition, information collected on the hepatic-safety CRF (where applicable) and a display of study drug exposure, adverse events, medications, blood pressure, heart rate, and the liver-related measurements over time will be provided for patients with information collected on the hepatic-safety CRF and any additional patients meeting ALT or AST measurement greater than or equal to 5X ULN (on a single measurement) or ALP measurement greater than or equal to 2X ULN (on a single measurement).
Treatment-Emergent Potential Hepatic Disorders Based on MedDRA SMQs: treatment-emergent potentially drug-related hepatic disorders are defined by using the MedDRA preferred terms contained in any of the following SMQs: 
 • Broad and narrow terms in the Liver related investigations, signs and symptoms SMQ (20000008) • Broad and narrow terms in the Cholestasis and jaundice of hepatic origin SMQ (20000009) • Broad and narrow terms in the Hepatitis noninfections SMQ (20000010) • Broad and narrow terms in the Hepatic failure, fibrosis and cirrhosis, and other liver damage SMQ (20000013)
Narrow terms in the liver-related coagulation and bleeding disturbances SMQ (20000015)

Abbreviations: ALP = alkaline phosphatase; ALT = alanine aminotransferase; AST = aspartate transaminase; CRF = case report form; MedDRA = Medical Dictionary for Regulatory Activities; SMQ = Standardized MedDRA Query; ULN = upper limit of normal; TBL = total bilirubin.

6.18.5.2. Hematologic Changes

Hematologic changes will be assessed through analysis of hemoglobin, white blood cell (leukocyte) count, absolute neutrophil count, lymphocyte count, and platelet count. Common Terminology Criteria for Adverse Events (CTCAEs) will be applied for laboratory tests potentially related to myelosuppressive events. The planned summaries are provided in [Table JAHV.6.16](#) and are described more fully in compound-level safety standards.

Table JAHV.6.16. Summary Tables Related to Hematologic Changes

Analysis
Shift tables showing the number and percentage of patients based on baseline to maximum will be created, with baseline depicted by the most extreme CTCAE grade during the baseline period. With each shift table, a summary displaying the number and percentage of patients who decreased, increased, or stayed the same in CTCAE grade category will be presented.
The number and percentages of patients with treatment-emergent shifts at any time will be summarized, based on any increase to CTCAE Grade 1 or above, Grade 2 or above, Grade 3 or above, and Grade 4 or above.
The number and percentages of patients with treatment-emergent thrombocytosis will be summarized, defined as an increase in platelet count from a maximum baseline value ≤ 600 billion/L to any postbaseline value >600 billion/L. Similar analysis will use a cut-off of 400 billion/L. Planned and unplanned measurements will be included.
Listing of patients with treatment-emergent thrombocytosis

Abbreviations: CTCAE = Common Terminology Criteria for Adverse Events.

